3.4 Recruitment

3.4.1 Initial Training

3.4.1a CHW Recruitment

[figure not shown]
CHWs ($n = 25$) will be recruited from the NGOs we are working with (please see above). Specifically, study team members will consult with supervisors at these NGOs to determine which CHWs may be able to participate in the training and incorporate the training content into their current job. Trained study team members will approach these CHWs, tell them about the training and study procedures, and ask if they would be interested in participating in the training. Participation (or lack thereof) will not affect the CHW's employment.

3.4.1b Patient Recruitment

At the training, CHWs will be asked to identify at least one and up to three patients with a history of HIV/TB co-infection who they suspect is depressed or struggling with substance use. CHWs will be asked to follow the scripts below with such patients:

1. Before the visit: Is it okay with you if I audio-record this session? This recording will be used by researchers at the SAMRC to help assess how I am doing my job, not to collect information about you. You may say yes or no—it will not affect your care. *If the patient says yes, the CHW will audio-record his/her interaction with the patient. If the patient says no, the CHW will continue with the session as usual. The patient will continue to receive their usual care from the CHW.*
2. At the end of the visit: Would you be willing to talk to a researcher from the SAMRC about your experience with this visit? This researcher will contact you and you will be compensated for your time spent answering these questions. *If the patient says no, the CHW will end the session as usual. If the patient says yes, the CHW will ask: Can I give the researcher your contact information? If the patient says yes, the CHW will pass on any relevant contact information (e.g., a phone number) to the study team. If the patient says no they do not want to have their details passed on but is willing to participate in the study, a researcher and the CHW will arrange to visit this patient together.*

Patients who agree to be contacted by a researcher and have a phone number, will be called by a researcher in the team. During this call, the researcher will

perform informed consent procedures with the patient and ask them some brief questions about themselves and the CHW visit.

For patients who agree to be asked questions by a researcher but do not agree for their contact details to be passed on or do not have a phone number to allow them to be interviewed telephonically, we will ask the CHW to arrange a suitable date and place for the researcher to meet the patient for a follow up interview. This will be a place where the patient feels comfortable and that can maintain confidentiality. If COVID-19 permits, we will offer patients the option of being transported to our project site in Delft where they can complete the interview. All procedures will follow usual CHW care processes and ways of engaging with particular patients so that their HIV status is not inadvertently disclosed to family members or others. Before the researcher meets the patient, the CHW will ask the patient if they are still interested in talking to the researcher and if now is a good time. If it is, the researcher will complete informed consent processes with the patient and ask them questions about themselves and the CHW visit. The CHW will be waiting away from the researcher and patient at this time so they cannot overhear what the patient says. If it is not a good time to complete these questions, the researcher will set a suitable time directly with the patient (should they still wish to participate in the study).

The patient recruitment process is illustrated in the Patient Recruitment figure.

3.4.2 Stepped-Wedge Trial

3.4.1. CHW Recruitment.

CHWs ($n=60$) will be recruited from the NGOs we are working with (please see Section 3.1.2 above). Specifically, study team members will consult with supervisors at our partner NGOs—who employ the CHWs—to determine which CHWs may be eligible to participate in the training and incorporate the training content into their current job (i.e., CHWs to see patients living with HIV/TB and may be struggling with depression and/or substance use). Trained study team members will approach these CHWs, tell them about the training and study procedures, and ask if they would be interested in participating in training. Participation (or lack thereof) will not affect the CHW's employment.

For qualitative interviews, a subset of CHWs (up to $n=20$) will be contacted from the organizations that participated in the training. Only CHWs who attended the training will be recruited for these interviews. CHW will be recruited across organizations and across change in stigma levels (improvement in stigma, no change in stigma, increase in stigma). Trained study team members will approach CHWs, tell them about the further study procedures, and ask if they would be interested in participating in the interview. Participation (or lack thereof) will not affect the CHW's employment.

3.4.2. Stakeholder recruitment

NGO leaders, policy makers and other stakeholders (up to $n=28$) will also be recruited. These stakeholders will be recruited after referral from health system leadership. Additionally, stakeholders who participated in Phase 1 interviews may be re-enrolled to participate in these follow-up interviews. Trained study team

members will approach stakeholders, tell them about the study procedures, and ask if they would be interested in participating.

3.5 Study Procedures

3.5.1 Initial Training

3.5.1a CHW Screening and Consent

Potentially eligible CHWs—referred to us by staff at partner NGOs—will be screened for eligibility. If they are eligible and interested in participating, they will undergo informed consent procedures. As part of this process, participants will be informed of all the potential risks and benefits to taking part in the study. Participants will be reminded that participation is voluntary, that they can decline to answer questions they are not comfortable answering, they are able to leave the study at any point, and that their decision to participate in the study will not impact their job. As part of signing the consent form, they will also consent to the Protection of Personal Information Act 4 of 2013. Upon giving willing, informed consent, they will then be invited to attend the training.

3.5.1b Training

Eligible and interested CHWs ($n = 25$) will be invited to attend a training on mental health and substance use. This training was adapted for this setting based on qualitative feedback collected from providers, stakeholders, and patients in our formative work, described in SAMRC Protocol #EC039-9/2020. It integrates two evidence-based training approaches: (1) information, defined as training to increase awareness and understanding of depression and SU in order to reduce stigma; and (2) motivation and behavior, defined as problem-solving therapy and motivational-interviewing for promoting re-engagement in care. More information on the specific training is provided in the training outline.

Training will be conducted in English, as the business language of the healthcare system. All CHW trainings offered by the Western Cape Department of Health that are required as part of their certification occur in English. Our training team, however, consist of isiXhosa and Afrikaans mother-tongue speakers and therefore will be able to address questions in these languages and facilitate roleplays in multiple languages should the need arise.

3.5.1c CHW Assessments

Pre-Assessment. Before the training begins, CHWs will complete a brief assessment. This assessment will include questions around demographics and stigma. It will also contain a brief roleplay vignette (approximately 10 minutes long) to assess pre-training competencies in psychological care, based on the ENACT stigma training,⁴⁵⁻⁴⁷ which will give us an estimate of how CHWs currently work with patients before attending our training. Finally, the assessment will include some questions to assess what CHWs already know about HIV, TB, depression, SU and stigma. We anticipate that this assessment will take about 40 minutes to complete.

Post-Assessment. On the last day of training, CHWs will complete another assessment with questions around stigma and knowledge of HIV, TB, depression, SU, and stigma. They will also complete another roleplay vignette based on the ENACT^{45,46} to assess competencies in psychological care and how they will work

with their patients after the training. Finally, they will self-complete surveys⁴⁸ to assess the training's feasibility and acceptability.

1-Month Follow-Up. Approximately one-month after the training—and one-month into receiving supervision—the CHWs will be asked to complete a final brief assessment. This assessment will contain the same questions around stigma, knowledge of HIV, TB, depression, SU, and stigma. It will also contain questions to assess the feasibility and acceptability of the supervision component of the training package.

3.5.1d Patient Recruitment

After the training, CHWs will return to their normal jobs and will be provided with the patient study eligibility criteria. CHWs will be asked to identify at least one patient and up to three patients who they believe fit eligibility criteria and that they think might be interested in (1) having their normal session audio-recorded and (2) if they would be interested in talking to a researcher at the MRC about the visit (for which they will be compensated). CHWs will be reminded of this in ongoing supervision. Please see the Patient Recruitment section for more details on this process.

3.5.1e Patient Assessment

Patients who agree to be contacted by a researcher and complete informed consent will be given a brief assessment where they are asked about demographic information, their HIV and/or TB, depression, and substance use. They will also be asked about their thoughts on their most recent CHW visit. Please note that informed consent will including consenting to the Protection of Personal Information Act 4 of 2013.

3.5.1f CHW Fidelity

CHW fidelity to the training will be measured in either or both of the following ways: through audio-recordings with real patients and through role-playing after the training.

- a) Audio-recordings with patients. Audio-recordings obtained by the CHWs will be assessed for fidelity to the training (i.e., skills taught that the CHW uses, correct information, and non-judgmental language). If a CHW obtains multiple audio-recordings, one audio-recording will be randomly selected to be assessed for fidelity.
- b) Roleplays. The roleplays in the post-assessment training will be videorecorded and will also be rated for fidelity to the training (i.e., skills taught that the CHW uses, correct information, and non-judgmental language, including non-judgmental nonverbal communication). Using roleplay information will (1) allow us to assess fidelity immediately after the training and (2) allow us to assess fidelity to the training even if CHWs are unable to later obtain audio-recordings of their actual sessions with patients.

3.5.1g CHW Supervision

Once a week for about a month, each CHW will have the opportunity to receive weekly small group supervision (n=5) with a registered psychological counselor. Supervision sessions will include feedback from fidelity checks, reminders from the three-day training, and role-playing of challenging patient interactions. There

will also be opportunities for clinical debriefing and psychosocial support for challenging patient interactions with a focus on problem solving. Role-plays may also be recorded at the end of some supervision sessions.

3.5.2 Stepped Wedge Trial

3.5.2a CHW Screening & Consent

Potentially eligible CHWs—referred to us by NGO staff will be screened for eligibility. If eligible and interested in participating, they will undergo informed consent procedures. As part of this process, participants will be informed of all the potential risks and benefits to taking part in the study. Participants will be reminded that participation is voluntary, that they can decline to answer any questions they are not comfortable answering, they can leave the study at any point, and their decision to participate in the study will not impact their job. As part of signing the consent form, they will also consent to the Protection of Personal Information Act 4 of 2013.

3.5.2b CHW Baseline and Pre-Training Assessments

Baseline Assessment. Upon giving willing, informed consent, CHWs will complete a baseline assessment with study staff. The baseline assessment will consist of self-report questions around CHWs' demographic characteristics and job, personal mental health questions, questions around knowledge of HIV, TB, depression and substance use, and questions around stigma.

Pre-Treatment Assessment. Immediately before their training, participants will complete a pre-training assessment. At this visit, participants will be asked to answer the same self-report questionnaires and as they did at baseline (with the exception of demographic and job information, which will not be asked again). All CHWs will also complete a brief (~10 minutes) role-play vignette with a staff member who is minimally involved in delivering the training, which will be videotaped and later coded for stigma using the ENACT.

3.5.2c CHW Training

After the baseline assessment all groups will receive at least one dose of TAU. Based on the training time to which their cluster was randomized, CHWs will then be invited to participate in a training on mental health and substance use.

Clusters randomized to Training Time #1 will receive the training first (while the other training times continue to receive TAU), followed by Training Time #2 (while the final training time continues to receive TAU), and finally, Training Time #3.

The training in the stepped-wedge trial will be the as the initial training, with minimal adaptations based on participant feedback (e.g., potentially an additional day, allocating more or less time to specific concepts, etc.). It will still be conducted in English, as all CHW trainings offered by the Western Cape Department of Health are required as part of the CHW certification occur in English. Roleplays will be conducted in English (training language) or isiXhosa (patients' language). Additionally, our training team consists of English, isiXhosa, and Afrikaans mother-tongue speakers; therefore, our team will be able to address questions and further explain concepts in these languages if needed.

3.5.2d CHW Post-Training Assessments

In addition to the Baseline and Pre-Treatment Assessments (which both occur before the training, and therefore, measure TAU), CHWs will also be required to complete two additional assessments after the training:

3-Month Follow-Up Assessment (3MFU): All participants will be invited to complete a follow-up assessment approximately 3-months after their training (3MFU). At this visit, participants will answer the same self-report questions they answered at the Pre-Training Assessment, answer additional questions about their perceived feasibility/acceptability of the training, and complete a roleplay for later ENACT coding.

6-Month Follow-Up Assessment (6MFU): All participants will also be invited to complete another follow-up assessment approximately 6-months after their training (6MFU). At this visit, participants will answer the same self-report questions they answered at the 3MFU and complete a roleplay for later ENACT coding. A subset of CHWs will also participate in semi-structured individual interviews in which they answer open-ended questions about their perceived feasibility/acceptability of the training.

3.5.2e Additional CHW Self-Report Measures

CHWs will complete the same measures during the stepped-wedge trial as they did in the initial training. In addition, they will also complete an integrated measure that assesses stigmas related to HIV and TB, which has been previously validated among health workers in South Africa.^{49,50} Additionally, the personal questions around personal mental health/ substance use will be slightly expanded upon (i.e., asking about self and friends in addition to family). Although there is not an immediate post-training assessment, participants will additionally do another roleplay on their last day of training, which will be rated using the ENACT.^{45,46} Please see Initial Training Procedures (above) for more information on the roleplay.

Based on feedback from the initial training, measures used in the initial training may also be shortened or slightly reframed (e.g., only asking the feasibility and acceptability subscales of the D&I measure).

3.5.2f Stakeholder Screening and Consent

Potentially eligible NGO leaders and stakeholders will be screened for eligibility. If eligible and interested in participating, they will undergo informed consent procedures. As part of this process, participants will be informed of all the potential risks and benefits to taking part in the study. Participants will be reminded that participation is voluntary, that they can decline to answer any questions they are not comfortable answering, they can leave the study at any point, and their decision to participate in the study will not impact their job. As part of signing the consent form, they will also consent to the Protection of Personal Information Act 4 of 2013.

3.5.2g Additional Measurements

Training Feasibility. CHW attendance in the training (less than one-week) and will be assessed as one measure of training feasibility. Over 75% of training sessions attending across all CHWs will be used as a benchmark for assessing whether the training is feasible.²

CHW Fidelity. To assess the fidelity of CHW delivery of training components (e.g., using non-judgmental communication, implementing MI/PST skills), 20% of the 3MFU roleplays will be randomly selected and rated using a fidelity assessment rating form in addition to being rated on the ENACT. A fidelity score will be calculated based on the proportion of key intervention components delivered as intended across the interactions based on these ratings.

NGO leader and stakeholder perceptions of feasibility and acceptability: Following the 6MFU assessment timepoint and collection of mixed-methods feasibility and acceptability data from CHWs, we will conduct qualitative interviews with leadership staff from NGOs, as well as policymakers and other stakeholders. These interviews will explore their perceptions of the feasibility and acceptability of the stepped-wedge training and aid in interpretation of data from CHWs themselves. Further, understanding organizational and systems barriers and facilitators to this training has important implications for longer term sustainment.

Patient Re-Engagement.

Chart Extraction. Chart extraction will be used to examine the rate of patient re-engagement in TB/HIV care. Specifically, data will be extracted from a centralized database of routinely collected data (*the Western Cape Province's Health Data Center*), which is hosted within the Western Cape Department of Health. The database includes information pertaining to demographic information, TB and HIV status, including whether TB and/or HIV treatment was initiated, date of initial diagnosis, lost-to-follow-up for TB and/or HIV care (i.e., missed treatment for two consecutive months), and date of TB and/or HIV treatment visits. This data is available by site and by unique patient health identification number (PHIN).

Around the time of a group's training, trained study researchers will receive a list of PHINs assigned to each CHW in the group in the past six-months from CHW supervisors/ workers overseeing CHWs. Aggregating data by CHW, and only viewing patients' PHIN and TB/HIV attendance data, we will extract whether patients re-engage, the time to re-engagement among those who return to care, and where patient re-engage in the six-months before the training.

Approximately six-months after a group's training, trained study researchers will receive a list of PHINs assigned to each CHW in the group since the training. Aggregating data by CHW, and only viewing patients' PHIN and TB/HIV attendance data, we will extract whether patients re-engage, the time to re-engagement among those who return to care, and where patient re-engage in the six-months before the training.

As only aggregate, de-identified data will be extracted from a centralized database, patients will not need to give informed consent.

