4.4 Secondary Preliminary Effectiveness Outcomes (Stepped-Wedge Trial Only)

4.4.1 Stepped-Wedge Trial

Re-engagement in TB/HIV care. The rate of patient re-engagement at the CHW level and time to re-engagement in TB/HIV care at the patient level in the six months prior to the CHW training compared to six-months following the CHW training will be evaluated using chart extraction. We will apply a Poisson regression model to compare rates of patient re-engagement at the CHW level, accounting for both clinic random effect and the fixed effect of time in the stepped wedge design. Pre-intervention patient re-engagement rates will be collected during the TAU phase for each clinic over the six months prior to the first CHW training, and post-intervention rates will be collected six months after the CHW training is complete via chart review. A Wald test will be used to test the effect of the CHW training intervention on the rates of patient re-engagement.

Time to re-engagement. To further investigate whether the CHW training intervention decreases patient time to re-engagement in TB/HIV care over six months, we will use a Cox Proportional Hazard survival model to model the patient-level outcome of time of re-engagement. Right censoring (those who do not re-engage within six months) is handled in the Cox model. A frailty model includes the random effect of clinics to account for unobserved heterogeneity. If the proportional hazard assumption is not met, the parametric accelerated failure time model can be used instead. We will control for amount of CHW contact with the patient (i.e., whether the CHW makes contact with the patient and the number of times the CHW visits the patient before the patient re-engages) and the patient's screening results (i.e., whether they screen positive for depression, hazardous alcohol use, and/or other drug use).

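### Section 3.5.2g takes post-training re-engagement from the six months before training, which contradicts Section 4.4.1; separately, the Cox model lists no calendar-time term

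*Combined protocol and SAP*

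**What the plan says.** Section 3.5.2g (Patient Re-Engagement, Chart Extraction) describes two extractions from the provincial database.

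- **First**, around the time of a group's training. Staff receive a "list of PHINs assigned to each CHW in the group in the past six-months" and extract whether patients re-engaged, plus "the time to re-engagement among those who return to care, and where patient re-engage in the six-months before the training".
- **Second**, about six months after the group's training. Staff receive a "list of PHINs assigned to each CHW in the group since the training". The outcome sentence is then the same, word for word, including its ending on the six months before training.

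The database fields named there include the "date of TB and/or HIV treatment visits". The date on which a patient was assigned to a CHW is not among them.

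Section 4.4.1 plans to evaluate re-engagement "in the six months prior to the CHW training compared to six-months following the CHW training". It adds that pre-intervention rates are "collected during the TAU phase for each clinic over the six months prior to the first CHW training" and that "post-intervention rates will be collected six months after the CHW training is complete via chart review". The Poisson model for CHW-level rates is fitted "accounting for both clinic random effect and the fixed effect of time in the stepped wedge design"; the unit and coding of time are not given. The Cox model for time to re-engagement has a clinic random effect (frailty) and adjusts for CHW contact and screening results. No calendar-time or step term is listed for it.

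**The concern.** Re-engagement in care is the only patient-level effectiveness outcome, and it is secondary (Section 1.2.2, objective c). Section 3.5.2g tells staff what to pull from the database. In the second extraction, the patients are defined by assignment after training and the outcome by a period before training. If that period applies to every item in the sentence, any re-engagement found would precede the patient's assignment to a trained CHW, and the post-training arm of the comparison would be empty.

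The time term is a separate matter. In a stepped wedge, training is correlated with calendar time by design, because every group moves from untrained to trained as the study goes on. A model without calendar time attributes any general drift in return to care to the training. As listed, the Cox/frailty model is in that position. The Poisson model is not, since it carries a fixed effect of time.

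**Working it through.** The plan states no figure for this point to reproduce: the 86% and 96% power in Section 3.3.2a concern the SDS. The check compares the texts and lays the windows on the calendar.

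**1. The two extractions side by side (Section 3.5.2g)**

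| | Patients listed | Outcome window printed | Window implied by Section 4.4.1 |
|---|---|---|---|
| First | assigned in the six months before training | six months before training | six months before training |
| Second | assigned since training | six months before training | six months following training |

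The first row agrees with itself and with Section 4.4.1. The second does neither, so the phrase is right where it first appears and wrong where it is repeated.

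**2. Size if the phrase governs the whole sentence**

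Input: training in months T = 5, 6 and 7 for Groups 1, 2 and 3 (Section 7, approximate). The printed window is months T−6 to T−1. The post-training period is T to T+5.

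- Group 1: printed −1 to 4; post-training 5 to 10; overlap 0 of 6
- Group 2: printed 0 to 5; post-training 6 to 11; overlap 0 of 6
- Group 3: printed 1 to 6; post-training 7 to 12; overlap 0 of 6

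Total overlap: 0 of 3 × 6 = 18 group-months.

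**3. What a trend could do to a model without calendar time (assumed illustration)**

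The documents give no trend. The mid-points of a group's pre and post windows are six months apart, so a hazard drifting upward by r per month gives an apparent hazard ratio of about (1+r)^6 with no training effect:

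- r = 0.5%: 1.005^6 = 1.03
- r = 1%: 1.01^6 = 1.06
- r = 2%: 1.02^6 = 1.13

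A downward trend would hide a benefit in the same way.

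**4. What time adjustment costs in precision**

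Take one value per group and month, equal weights, and each group's own windows: 36 group-months, or 33 if the training month is dropped as transition. The variance ratio is the residual sum of squares of the training indicator without time, divided by that with time. The standard error grows by its square root. The second figure in each pair includes clinic fixed effects.

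| Time term | Training month | Variance ratio | Standard error multiplied by |
|---|---|---|---|
| Categorical month | counted as post | 9/1.333 = 6.75; 9/1.143 = 7.88 | 2.6; 2.8 |
| Linear month | counted as post | 9/2.563 = 3.51; 9/2.203 = 4.09 | 1.9; 2.0 |
| Categorical month | dropped | 8.182/0.500 = 16.4; 8.182/0.444 = 18.4 | 4.0; 4.3 |
| Linear month | dropped | 8.182/1.899 = 4.31; 8.182/1.576 = 5.19 | 2.1; 2.3 |

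These are least-squares ratios for the layout of windows. They are a guide to the Poisson and Cox models, not a prediction of their standard errors.

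**The case against.** **The slip corrects itself.** The list is drawn six months after training for patients assigned since training, so a pre-training window makes no sense there. Section 4.4.1 is also a collection rule, not only an analysis plan, and it places the post-intervention rates after training. Anyone who reads both sections would probably use the right window. This stands as an argument about likely harm. It does not remove the contradiction: Section 3.5.2g gives the detailed extraction steps, and no other passage corrects it.

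**The reach of the phrase is uncertain.** The sentence lists three items: whether patients re-engage, how long it takes, and where. The time phrase may attach only to the last. This also stands. The phrase is wrong under either reading, but the 0 of 18 overlap applies to the whole outcome only under the wider one.

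**The pre-training wording is not an error.** A reader might infer that the trial's first training sets one common pre-window. The words tying the window to each clinic make that clinic's own training the natural reading, and Section 3.5.2g and the opening of Section 4.4.1 agree with it.

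**The Poisson model already has time.** A reader might infer that training cannot be separated from time because the data are one pre and one post total per CHW. No passage says so. Visit dates are in the database, and time coded only as pre and post would merely duplicate the training term. What remains is that the unit of time is not stated.

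**The trend is hypothetical.** That is correct. The hazard ratios above show sensitivity and are not evidence of bias in this trial.

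**Conclusion.** The second extraction in Section 3.5.2g is wrong as written and should be corrected. That much is certain from the text. Its size depends on grammar. If the phrase covers the whole sentence, 0 of 18 post-training group-months are captured, given training in months 5, 6 and 7. If it covers only the last item, just the location of re-engagement is misdirected. A reader might conclude that post-training data will be lost. The documents do not support that, because Section 4.4.1 states the intended period; the likely harm is an extraction rule at odds with the analysis.

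The pre-training wording in Section 4.4.1 needs clarifying and is not an error.

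The missing calendar-time term in the Cox/frailty model is a cheap improvement rather than a fault of the same kind. Its effect depends on a trend that the documents do not give. It does not extend to the Poisson model as described, beyond the undefined unit of time. The primary SDS outcome and its power are untouched.

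**What to change.** 1. **Section 3.5.2g, second extraction only:** change the closing phrase to *in the six months after the training*. Leave the first extraction as it is. This is a wording change with no loss.
2. **Section 4.4.1, pre-intervention rates:** refer to the six months prior to *each group's own training*. This is also wording only.
3. **Section 4.4.1, models:** state calendar month as the time effect in the Poisson model, and add calendar period to the Cox/frailty model. Alternatively, label any pre/post contrast without time adjustment as descriptive, which is acceptable in a pilot.

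Item 3 has two costs. The interval widens: the standard error is about 1.9 to 2.8 times larger with monthly counts and own-training windows, or 2.1 to 4.3 times larger if training months are transition. The smaller values in each range come from assuming a linear trend. The supervisors' patient lists would also need assignment dates. These must be checked against Section 3.5.2g's ground for not seeking patient consent, namely that the extracted data are aggregated and carry no identifiers.

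Under Section 6.2.2, all protocol changes go to the ethics committee before they are implemented, so the three items are best submitted together.
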